8.1.3. Population of Interest

The primary pharmacodynamics analyses will be based on the PDPP population, unless otherwise specified.

8.1.4. Strategy for Intercurrent (Post-Randomization) Events

Due to the design of the PDPP population, only subjects who have FBF measurements for both Day 1 and Day 42 are included, and it is not possible to have missing FBF data. Therefore, no FBF data will be imputed.

8.1.5. Statistical Analyses / Methods

Details of the planned displays are provided in [Appendix 10](#): List of Data Displays and will be based on GSK Data Standards and statistical principles.

Unless otherwise specified, endpoints / variables defined in Section [8.1.1](#) will be summarised using descriptive statistics and listed.

8.2. Secondary Pharmacodynamic Analyses

8.2.1. Endpoint / Variables

- Principle secondary endpoint: change in the absolute FBF
- Secondary endpoints:
 - FBF ratio, absolute FBF of Sodium nitroprusside and L-NMMA
 - Augmentation index
 - PWV

Absolute FBF is defined as only including the FBF value from the subject's treatment arm which is infused with either saline or challenge agents.

8.2.2. Summary Measure

Principle secondary endpoint: Change in the absolute FBF from Day 1 to Day 42 in response to acetylcholine

Secondary endpoints: Change in FBF ratio from Day 1 to Day 42 in response to sodium nitroprusside and L-NMMA.

Change in absolute FBF from Day 1 to Day 42 in response to sodium nitroprusside and L-NMMA.

Change in Augmentation Index (AIX, an indicator of arterial stiffness) as estimated by radial arterial pulse contours from Day 1 to Day 42.

Change in pulse wave velocity (PWV) from Day 1 to Day 42.

For the PWV dataset, there are two recorded values for each variable per day, with the option to collect a third value if the first two values varied (Refer: SRM) too much from each other. The average of the two closest absolute values will be used for analysis purposes.

If for any of these measures mentioned above, the respective procedures are repeated for Day 1 and/or Day 42, the data from the repeat visit will take place of the original Day 1 and Day 42 data respectively. Like the FBF data, a QC check will be performed for the PWV data before the final analyses. The QC check will be to assess negative and extreme values for PWV ([PWV](#)).

Descriptive statistics (n, mean, standard deviation (SD), minimum, median, maximum) will be calculated by treatment group.

8.2.3. Population of Interest

The secondary pharmacodynamics analyses will be based on the PDPP population, unless otherwise specified.

8.2.4. Strategy for Intercurrent (Post-Randomization) Events

Augmentation index and PWV data is expected to have minimal missing data, therefore these data points will not be imputed if missing.

8.2.5. Statistical Analyses / Methods

Details of the planned displays are provided in [Appendix 10](#) List of Data Displays and will be based on GSK Data Standards and statistical principles.

Unless otherwise specified, endpoints / variables defined in Section [8.2.1](#) will be summarised using descriptive statistics and listed.

CONFIDENTIAL

205767

10. APPENDICES

10.1. Appendix 1: Protocol Deviation Management and Definitions for Per Protocol Population

10.1.1. Exclusions from Per Protocol Population

There is no important protocol deviation identified in the study, hence no exclusions for per protocol population.

CONFIDENTIAL

205767

10.2. Appendix 2: Schedule of Activities

10.2.1. Protocol Defined Schedule of Activities

Procedure	Screening ¹	Treatment Period ²						Follow-up ³
	Up to 30 Days	Day 1	Repeat Day 1 ¹⁷	Day 14	Day 28	Day 42	Repeat Day 42 ¹⁷	
Informed consent	X							
Eligibility Criteria	X	X ⁴						
Physical examinations, Medical History, Demographics	X	X ⁵						
HemoCue Hgb	X	X ⁶	X	X	X	X	X	
eGFR	X							
Vital signs	X	X ⁶	X	X	X	X	X	X
Clinical chemistry ⁷	X					X		X
Hematology ⁷	X	X		X	X	X		X
Serum pregnancy test (FRP only)	X							
Urine pregnancy test (FRP only) ⁸		X	X	X	X	X	X	X
Folate & Vitamin B ₁₂	X							
12 Lead ECG	X	X ⁶				X		X
Ferritin & TSAT	X							
hs-CRP	X	X				X		
Females only: FSH ⁹	X							
5Brachial artery palpation	X							
Randomization		X						
Daprodustat administration ¹⁰		<=====>						
Darbepoetin alfa administration ¹⁰		X ¹⁰		X	X	See footnote 18		

CONFIDENTIAL

205767

Procedure	Screening ¹	Treatment Period ²						Follow-up ³
	Up to 30 Days	Day 1	Repeat Day 1 ¹⁷	Day 14	Day 28	Day 42	Repeat Day 42 ¹⁷	
Study treatment adjustment ¹¹					X			
Liver chemistry monitoring				X	X			
International Normalized Ratio (INR) ¹²	X	X	X			X	X	
Hepatitis B and C screening ¹³	X							
HbA1c, lipids ⁷		X						
Forearm Blood Flow (FBF) ¹⁴		X	X			X	X	
Pulse Wave Velocity (PWV) ¹⁴		X	X			X	X	
AE and SAE Assessment	X ¹⁵	X	X	X	X	X	X	X
Blood draw for storage biomarkers ¹⁶		X				X		
Review concomitant medications	X	X	X	X	X	X	X	X

¹ All participants will undergo screening assessments within 30 days of enrolment.

² Allowable time window \pm 2 days except for the forearm blood flow (FBF) & pulse wave velocity (PWV) as noted.

³ Allowable time window \pm 3 days. Follow up will occur 7-14 days \pm 3 following completion of the last FBF procedure. See Section 8.2 for guidance regarding EW participants.

⁴ Eligibility criteria to be assessed prior to performance of the FBF procedure include HemoCue hemoglobin (Hgb), vital signs & 12-lead electrocardiogram (ECG).

⁵ Only a brief physical exam on Day 1.

⁶ As detailed in Exclusion Criteria (Section 6.2).

⁷ Clinical chemistry, hematology and other laboratory tests as listed in Appendix 2.

⁸ Local urine pregnancy testing will be standard for protocol unless serum testing is required by local regulations or Institutional Review Board (IRB)/ Independent Ethics Committee (IEC).

⁹ As detailed in Inclusion Criteria (Section 6.1).

¹⁰ The initial dose of study treatment will be **after** the Day 1/Repeat Day 1 FBF & PWV procedures. Participants will receive **EITHER** daprodustat **OR** darbepoetin alfa.

The final dose of daprodustat will be Day 41 (i.e., the day prior to the FBF & PWV procedures), while the final dose of darbepoetin alfa will be Day 28. If repeat procedures are needed the dosing will be extended (See Section 9.6.1.4).

CONFIDENTIAL

205767

¹¹ See Section 7.2 for details on study treatment adjustment

¹² Applies only to participants on anti-coagulant therapy; further details concerning measurement of the international normalised ratio (INR) and subsequent actions can be found in the study reference manual (SRM).

¹³ If test otherwise performed within 3 months prior to first dose of study treatment, testing at screening is not required

¹⁴ The FBF & PWV assessments are to be performed following confirmation of INR < 3.0 for participants on anticoagulant therapy. The Day 42 FBF & PWV assessments can be delayed up to 1 week (i.e., Day 49), while randomization (Day 1) should be delayed until the participant's INR < 3.0 (Section 9.6.1.1).

¹⁵ Only serious adverse events (SAEs) assessed as related to study participation are collected at this visit. See [Appendix 4](#) for additional details.

¹⁶ As described in Section 9.8

¹⁷ Indicates the procedures to be performed on the repeat visits only if the visit is deemed necessary. See Section 9.6.1.4.

¹⁸ Darbepoetin is only to be given on Day 42 if a Repeat Day 42 is needed.

CONFIDENTIAL

205767

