¹⁰The initial dose of study treatment will be given **after** the completed Day 1/Repeat Day 1 FBF & PWV procedures. Participants will receive **EITHER** daprodustat **OR** darbepoetin alfa. The final dose of daprodustat will be Day 41 (i.e., the day prior to the FBF & PWV procedures), while the final dose of darbepoetin alfa will be Day 28. If repeat procedures are needed the dosing will be extended (See Section 9.6.1.4).

¹¹See Section 7.2 for details on study treatment adjustment

¹²Applies only to participants on anti-coagulant therapy; further details concerning measurement of the international normalised ratio (INR) and subsequent actions can be found in the study reference manual (SRM).

¹³If test otherwise performed within 3 months prior to first dose of study treatment, testing at screening is not required

¹⁴The FBF & PWV assessments are to be performed following confirmation of INR < 3.0 for participants on anticoagulant therapy. The Day 42 FBF & PWV assessments can be delayed up to 1 week (i.e., Day 49), while randomization (Day 1) should be delayed until the participant's INR < 3.0 (Section 9.6.1.1).

¹⁵Only serious adverse events (SAEs) assessed as related to study participation are collected at this visit. See Appendix 4 for additional details.

¹⁶As described in Section 9.8

¹⁷Indicates the procedures to be performed on the repeat visits only if the visit is deemed necessary. See Section 9.6.1.4

¹⁸Darbepoetin is only to be given on Day 42 if a Repeat Day 42 is needed.

- The timing and number of planned study assessments, including: safety, pharmacodynamic or other assessments may be altered during the course of the study based on newly available data (e.g., to obtain data closer to the time of peak plasma concentrations) to ensure appropriate monitoring.
- Any changes in the timing or addition of time points for any planned study assessments must be documented and approved by the relevant study team member and then archived in the sponsor and site study files, but will not constitute a protocol amendment. The IRB/IEC will be informed of any safety issues that require alteration of the safety monitoring scheme or amendment of the ICF.

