9.6.1.4. Delayed or Repeat FBF Procedures

Delayed FBF Procedures: In the instance that the FBF procedure needs to be delayed, participants should either continue receiving the daprodustat dispensed on Day 28, while the participants randomized to darbepoetin alfa should receive an appropriate dose on Day 42. The assessments that are scheduled to be conducted on Day 42 are to be followed (See Section 2).

Repeat FBF Procedures: If the FBF procedure is determined to be repeated for either Day 1 or Day 42, the assessments should be performed as per the SoA Table at the additional FBF visit. The PWV procedures should also be repeated.

In the instance that the Day 1 FBF procedure needs to be repeated, the participant should not be dosed with study drug until after the repeat/completed procedure. The timing of all subsequent visits will begin from that completed procedure day.

In the instance that the Day 42 FBF procedure needs to be repeated, participants should either continue receiving the daprodustat dispensed on Day 28, while the participants randomized to darbepoetin alfa should receive an appropriate dose on Day 42. The safety follow up visit will take place 7-14 days after the final procedure.

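### For a Day 42 FBF that is delayed but not repeated, the schedule footnotes and protocol Section 9.6.1.4 give conflicting dosing instructions, so exposure before the primary measurement depends on which text a site follows

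*SAP*

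**What the plan says.** **Delay is a planned route.** Footnote 14 of the schedule of activities (protocol Section 2) states: "The Day 42 FBF & PWV assessments can be delayed up to 1 week (i.e., Day 49"). Protocol Sections 9.6.1.1 (INR of 3.0 or more), 9.4.2 (systolic pressure above 170 or diastolic above 100 mmHg) and 9.4.3 (abnormal ECG, at the investigator's discretion) each allow it, and each refers to Section 9.6.1.4 for details.

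**The schedule.** Footnote 18 states: "Darbepoetin is only to be given on Day 42 if a Repeat Day 42 is needed". Footnote 10 names Day 41 as the last daprodustat dose, continues "while the final dose of darbepoetin alfa will be Day 28", and then adds the only extension: "If repeat procedures are needed the dosing will be extended (See Section 9.6.1.4"). SAP Section 10.2.1 reproduces both footnotes.

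**Section 9.6.1.4.** This section treats delayed and repeat procedures under separate labels. On daprodustat in the delayed case it says: "In the instance that the FBF procedure needs to be delayed, participants should either continue receiving the daprodustat dispensed on Day 28". The instruction for the comparator arm in that case reads: "while the participants randomized to darbepoetin alfa should receive an appropriate dose on Day 42". It also sends a delayed procedure to the ordinary Day 42 column of the schedule: "The assessments that are scheduled to be conducted on Day 42 are to be followed". The same dosing text appears again for a repeated Day 42 procedure.

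**The concern.** The word limiting footnote 18 to a Repeat Day 42 leaves no room for a delay. A delayed FBF is not a Repeat Day 42: it follows the Day 42 assessments, while Repeat Day 42 has its own column. For a delayed, non-repeated FBF, one text therefore withholds the Day 42 darbepoetin dose and the other gives it. Footnote 10 has a matching gap for daprodustat.

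The primary endpoint is the change in the acetylcholine FBF ratio from Day 1 to Day 42, so exposure just before the second measurement is part of the treatment contrast. If sites read the texts differently, participants in the same arm reach that measurement with different dose counts and different times since the last dose. FBF data are summarised by scheduled visit (SAP Section 10.3.1), and the Listing 17 shell has no dosing-interval column, so a reader of that listing could not see the difference.

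**Working it through.** The plan states no figure on this point. The check sets the texts side by side and counts days.

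**Inputs**
- Darbepoetin on Days 1, 14 and 28; last daprodustat dose on Day 41 (protocol Section 2, footnote 10, and Section 7).
- A delayed FBF falls on day *f*, with *f* from 43 to 49 (footnote 14).
- A Day 42 darbepoetin dose: no under footnote 18, yes under Section 9.6.1.4.
- Assumptions: nominal visit days, no dose held, no repeat procedure.

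**Darbepoetin**
- Undelayed: 3 doses; 42 − 28 = 14 days from last dose to FBF.
- Delayed, footnote 18: 3 doses; interval *f* − 28.
- Delayed, Section 9.6.1.4: 4 doses (Days 1, 14, 28, 42); interval *f* − 42.

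| FBF day | Footnote 18 | Section 9.6.1.4 | Difference |
|---|---|---|---|
| 43 | 43 − 28 = 15 days | 43 − 42 = 1 day | 14 days |
| 46 | 46 − 28 = 18 days | 46 − 42 = 4 days | 14 days |
| 49 | 49 − 28 = 21 days | 49 − 42 = 7 days | 14 days |

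The gap is (*f* − 28) − (*f* − 42) = 14 days and one dose, whatever the day of the delayed FBF.

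**Daprodustat**
- Undelayed: 42 − 41 = 1 day from last dose to FBF.
- Delayed, footnote 10 read literally: dosing stops at Day 41, so the interval is *f* − 41, from 43 − 41 = 2 to 49 − 41 = 8 days.
- Delayed, Section 9.6.1.4: dosing continues. If the last tablet is taken the day before the FBF (an assumption), the interval is 1 day.
- Footnote 10 also describes its Day 41 as the day before the procedures. That could be read as moving with the delay, in which case the texts agree. The footnote does not settle which reading is meant.

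**Repeat procedures.** For a repeated Day 42 FBF, footnotes 10 and 18 and Section 9.6.1.4 agree that dosing is extended. The contradiction is confined to the delayed, non-repeated case.

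**Knock-on for safety.** SAP Section 10.4.2 counts an adverse event as treatment-emergent up to the treatment stop date plus 1 day. If the darbepoetin stop date is the date of the last injection (an assumption), the window closes on 28 + 1 = Day 29 or on 42 + 1 = Day 43, a shift of 14 days.

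**The case against.** The strongest reply is that a site handling a delay would in practice reach Section 9.6.1.4. All three delay routes point there, it has a paragraph for exactly this case, and protocol Section 9 describes the schedule as a summary. On that view footnotes 10 and 18 merely omit a case. This lowers the chance of divergent practice but does not remove the contradiction: footnote 18 is a restrictive dosing instruction in the table that sites work from, not a silence.

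Second, unequal exposure exists anyway. A repeated FBF follows a fourth darbepoetin dose under every text, and Section 7.1.1.2 allows doses to be held or delayed. This is correct. Reconciling the wording would remove one source of spread, not all of it.

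Third, the study was terminated. SAP Section 2.1 reports 4 completers and summary statistics only, and Section 10.1.1 records no important protocol deviation. This stands and limits the practical weight.

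Two stronger readings are tempting and are not supported:
- A reader might infer that only the darbepoetin arm is affected, because Section 9.6.1.4 continues daprodustat. But footnote 10 extends dosing beyond Day 41 only for repeats, and Section 7 also ends daprodustat at Day 41. The inconsistency can touch both arms.
- A reader might infer that the primary comparison is biased, especially since high blood pressure triggers delay and Section 5.4 links the six-week duration to blood pressure rises with rhEPO. The documents do not show that delays would differ by arm, how many there would be, or how FBF varies with time since dosing. Neither the direction nor the size of any bias can be derived.

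**Conclusion.** The point holds as an internal contradiction in an operative dosing rule. For a delayed, non-repeated Day 42 FBF, a darbepoetin participant has either 3 doses with the last 15 to 21 days earlier, or 4 doses with the last 1 to 7 days earlier. For daprodustat the schedule is at best ambiguous: read literally, it leaves 2 to 8 days without drug before the FBF, where Section 9.6.1.4 continues dosing.

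These figures rest on the nominal visit days and the assumptions listed above. The number of participants affected is not given, so no effect on the treatment comparison can be calculated. With 4 completers and no between-arm testing, the consequence in this study is likely to be small. What remains is whether the record is coherent and the FBF listing can be interpreted. This review takes no position on which dosing instruction is right.

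**What to change.** 1. **Reconcile the texts.** Footnotes 10 and 18 of the protocol schedule, Section 9.6.1.4 and the SAP copy should give one instruction per arm for a delayed FBF. The final-dose statement in Section 7 should be checked against it. The choice belongs to the sponsor and the investigators. The wording change is short, but under Appendix 3 a protocol amendment needs ethics approval. If the terminated study will not be amended, the clinical study report can state the discrepancy and what was done for any delayed participant, and the text can be corrected before the design is reused.

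2. **Show days since last dose in Listing 17,** beside each Day 42 or Repeat Day 42 FBF. This applies a rule already in SAP Section 10.5.2, under which listings show actual as well as planned time from dosing. It costs one derived column. For darbepoetin, protocol Section 7.6 requires details of each supervised dose to be kept. For daprodustat the source needs checking: protocol Section 7.6 says stop dates go in the eCRF, while SAP Section 10.6.2 says no exposure end date was collected.

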10.3. Appendix 3: Assessment Windows

10.3.1. Definitions of Assessment Windows for Analyses

Data for continuous variables will be summarized according to the scheduled visit time period for which they were recorded in the eCRF. Unscheduled assessments will not be slotted to a particular time point but will remain as unscheduled if they are either summarized or listed unless otherwise specified.

CONFIDENTIAL

205767

10.4. Appendix 4: Study Phases and Treatment Emergent Adverse Events

10.4.1. Study Phases

Assessments and events will be classified according to the time of occurrence relative to study treatment start and stop dates.

Study Phase	Definition
Pre-Treatment	Date < Study Treatment Start Date
On-Treatment	Study Treatment Start Date ≤ Date ≤ Study Treatment Stop Date + 1 day
Post-Treatment	Date > Study Treatment Stop Date + 1 day

- If the treatment stop date is missing and the treatment start date is non-missing, then the assessment will be considered On-Treatment.

10.4.1.1. Study Phases for Concomitant Medication

Study Phase	Definition
Prior	If medication end date is not missing and is before 28 days prior to screening visit
Concomitant	Any medication that is not a prior

NOTES:

- Please refer to [Appendix 7: Reporting Standards for Missing Data](#) for handling of missing and partial dates for concomitant medication. Use the rules in this table if concomitant medication date is completely missing.

10.4.2. Treatment Emergent Flag for Adverse Events

Flag	Definition
Treatment Emergent	
 • If AE onset date is on or after treatment start date & on or before treatment stop date + 1 day • Study Treatment Start Date ≤ AE Start Date ≤ Study Treatment Stop Date + 1 day

NOTES:

- If the study treatment stop date is missing, then the AE will be considered to be On-Treatment.
- Time of study treatment dosing and start/stop time of AEs should be considered, if collected.

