5. STUDY DESIGN

5.1. Overall Design

This study will use a randomized, repeat dose, open label, parallel group design, in adult, ND, male and female participants with anemia of CKD that are currently not treated with rhEPOs (i.e. no rhEPO use within the 12 weeks prior to the screening visit and through Day 1). The study design is outlined in [Figure 1](#).

- The study will comprise three study periods: a screening period starting up to 30 days prior to Day 1, a 42 day (6 week) treatment period with 4 visits starting at Day 1, and a follow-up visit up to 14 days later ([Figure 1](#)). The total duration of participant involvement is up to 14 weeks.
- Participants will be randomized to either daprodustat or darbepoetin alfa. A central randomization approach will be used with stratification by center.
- All participants will be treated with the goal of achieving a Hgb level within the range of 10.0 to 12.0 g/dL, consistent with national guidelines ([Medicines and Healthcare Products Regulatory Agency, 2007](#)).
- FBF and PWV will be conducted at the beginning (Day 1) and end (Day 42) of the treatment period as outlined in the SoA (See [Section 2](#)) and described in [Section 9.6](#).
- This study will include an optional, Non-Contact, Optical Forearm Plethysmography (NC-OFPP) Sub-Study (See [Appendix 8](#)).

Figure 1 Study Outline

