7. TREATMENTS

Study treatment is defined as any investigational treatment(s), marketed product(s), placebo, or medical device(s) intended to be administered to a study participant according to the study protocol. Eligible participants will be randomized to receive **either** daprodustat or darbepoetin alfa.

Participants randomized to daprodustat will receive this study treatment daily, starting Day 1 through Day 41 (i.e., day prior to FBF & PWV procedures). Participants randomized to darbepoetin alfa will receive this study treatment every 2 weeks, starting Day 1 through Day 28.

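### The SAP closes the on-treatment and treatment-emergent window one day after the last dose in both arms, so a darbepoetin participant dosed to schedule leaves it at Day 29 and a daprodustat participant at Day 42

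*SAP*

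**What the plan says.** SAP 10.4.1 sets the scope of the phases: "Assessments and events will be classified according to the time of occurrence relative to study treatment start and stop dates". On-treatment is "Study Treatment Start Date ≤ Date ≤ Study Treatment Stop Date + 1 day", and post-treatment is "Date > Study Treatment Stop Date + 1 day". SAP 10.4.2 uses the same end point for adverse events: "If AE onset date is on or after treatment start date & on or before treatment stop date + 1 day". Neither section has a version for each arm, and no arm-specific lag appears elsewhere in the SAP.

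The two drugs have different schedules. SAP 10.2.1 states "The final dose of daprodustat will be Day 41". Footnote 10 to the protocol's Schedule of Activities continues "while the final dose of darbepoetin alfa will be Day 28". Protocol section 7 agrees: "Participants randomized to darbepoetin alfa will receive this study treatment every 2 weeks, starting Day 1 through Day 28".

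The protocol nevertheless gives both arms one treatment period. Section 5.1 describes "a 42 day (6 week) treatment period with 4 visits starting at Day 1" and places the second forearm blood flow (FBF) procedure at its end, on Day 42. Section 7.7.4 spells the period out as Day 1 to Day 42.

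**The concern.** A one-day lag suits a daily tablet because it covers one dosing interval. Applied to an injection given every 14 days, it closes the window at the start of the last interval. The protocol counts Day 28 to Day 42 as treatment time for both arms; the SAP's labels count most of it as treatment time for daprodustat only.

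What is at stake is whether the flag means the same thing in each arm. An event starting on Day 35 would be treatment-emergent on daprodustat and not on darbepoetin, with the same time since randomisation and both participants dosed to schedule. Anyone who later counts or pools events by this flag would be using windows of different length without being told.

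**Working it through.** The plan states no figure to reproduce. The check is day arithmetic on its own rules, reading the stop date as the date of the last dose.

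**Inputs.** Lag of 1 day (SAP 10.4.1 and 10.4.2). Last scheduled dose: Day 41 for daprodustat, Day 28 for darbepoetin (SAP 10.2.1; protocol sections 2 and 7). Treatment period: Days 1 to 42 (protocol 5.1 and 7.7.4).

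**1. Participant dosed to schedule.** Last on-treatment day = last dose day + 1.

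- Daprodustat: 41 + 1 = Day 42. On-treatment days: 42 of 42.
- Darbepoetin: 28 + 1 = Day 29. On-treatment days: 29 of 42. Days 30 to 42 are post-treatment: 42 − 29 = 13 days, and 13/42 = 31%.

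**2. Visit window.** If the Day 28 visit moves by the permitted 2 days either way, the last injection falls on Days 26 to 30 and the window ends on Days 27 to 31. A final visit anywhere from Day 40 to Day 44 is still labelled post-treatment.

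**3. Delayed or repeat Day 42 procedure (protocol 9.6.1.4).** Darbepoetin is then given on Day 42 and daprodustat continues. Take a procedure on Day 49 with daprodustat taken to Day 48:

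- Daprodustat: 48 + 1 = Day 49, so the visit is on-treatment.
- Darbepoetin: 42 + 1 = Day 43. Day 42 is now on-treatment, but the Day 49 visit is not.

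**4. Meaning of the stop date.** The SAP does not define it. SAP 10.6.2 says no exposure end date is collected and assigns one day to each dose date, which supports reading it as the last dose date. Protocol 7.6 says stop dates are recorded in the eCRF. If the stop date were treated as missing, the fallbacks in SAP 10.4.1 and 10.4.2 would label everything after the start as on-treatment in both arms, follow-up included. The arms would then match, but the window would have no end.

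**5. Where the labels are used.**

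- SAP 10.3.1 summarises continuous data by scheduled visit.
- SAP 10.10.5 lists tables for laboratory values, ECG and vital signs, and none for adverse events.
- SAP 7.1 and 10.10.7 plan adverse event listings on the Safety population, with no stated restriction to treatment-emergent events.

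**6. Would a flat one-interval lag be enough?** For a participant dosed to schedule, yes: 28 + 14 = Day 42. Elsewhere it fails. An injection on Day 26 gives 26 + 14 = Day 40, before a Day 42 visit. An extra injection on Day 42 gives 42 + 14 = Day 56, against Day 49 for daprodustat in step 3. The window for completers therefore needs to be tied to the visit.

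**The case against.** The strongest case against is that nothing planned depends on the flag. The SAP is a close-out plan for a terminated study with 4 completed subjects and descriptive output only (SAP 2.1). All adverse events are listed whatever their flag, and the objective is to assess safety, with no formal safety analysis (protocol 10.3.2). This stands, and it limits the point to labels.

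Two stronger readings are tempting. The documents support neither.

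- A reader might infer that the darbepoetin arm's Day 42 FBF data are lost or set apart, or that the label contradicts the estimand of six weeks of randomised treatment (SAP 2.4). The pharmacodynamic population is defined by having Day 1 and Day 42 data, the displays compare those visits, and no rule excludes or splits data by phase. The phase label does not enter the primary summary.
- A reader might infer that daprodustat will show 42/29 = 1.45 times as many treatment-emergent events with no true difference. That assumes equal, uniform event onset over Days 1 to 42 and a table that counts flagged events. No such table is planned, and 4 completers could not show such a ratio reliably.

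It can also be said that the asymmetry disappears if the stop date is missing. That is true, but only because the window then has no end. It shows that the stop date needs a definition, not that the rule works.

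**Conclusion.** The rule is wrong as written and worth correcting, but its effect is small. With the stop date read as the last dose date, a darbepoetin participant dosed to schedule is on treatment for 29 days and a daprodustat participant for 42. The 13 days of difference fall inside the protocol's treatment period. Darbepoetin events with onset on those days are not flagged; daprodustat events are.

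The effect stops at the phase labels and the treatment-emergent flag in the analysis datasets, and any adverse event reporting that draws on them. Day 42 pharmacodynamic and safety summaries are unaffected. The day counts assume dosing to schedule; an extra Day 42 injection shifts them as shown in step 3. The reading of the stop date is the better supported one, but the SAP leaves it open.

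**What to change.** Make two changes in SAP 10.4.1 and 10.4.2.

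1. **Define the stop date** as the last recorded dose date, and reconcile protocol 7.6 with SAP 10.6.2 on whether that date is collected. State that the missing-stop-date fallback does not apply to participants with recorded doses.
2. **Use one analysis window for both arms**, starting at the first dose:
   - Participants who complete treatment: through the later of last dose + 1 day and the Day 42 visit, or the delayed or repeat Day 42 visit where there is one.
   - Participants who stop early: through last dose plus one dosing interval, that is + 1 day for daprodustat and + 14 days for darbepoetin.

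For completers, both arms then close on Day 42 when dosed to schedule, and on Day 49 in the repeat example. The one-interval lag for early stoppers is a convention, and the SAP should state it as one.

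The cost is a few lines of text and one arm-specific derivation, with no new assessments. A few late darbepoetin events may become treatment-emergent. The change affects analysis labels only, not dosing.
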